5. STUDY TREATMENTS

5.1. Description, Storage, Packaging, and Labeling

The Sponsor (or designee) will provide the Investigator (or designee) with adequate quantities of LOXO-305. Covance will procure adequate quantities of caffeine, omeprazole, warfarin, and vitamin K (Table 2).

Table 2: Study Drugs

Study Drug	Form ^a	Strength	Supplier	Manufacturer ^b
LOXO-305	Tablet	2 × 100 mg	Loxo Oncology, Inc.	Catalent San Diego or Lonza Pharma & Biotech
Caffeine	Tablet	200 mg	McKesson	Meda Consumer Health
Omeprazole	Capsule	40 mg	McKesson	Sandoz
Warfarin	Tablet	10 mg	McKesson	Taro
Vitamin K	Tablets	2 × 5 mg	McKesson	Valeant Pharmaceuticals

^a Specific ingredients/purity will be identified in the Certificate of Analysis (or equivalent) that is supplied with the study drug(s).

^b The manufacturer will be confirmed by the site at the time of drug procurement.

The tablets containing 100 mg LOXO-305 will be supplied by the Sponsor (or designee), along with the batch/lot numbers and Certificate of Analysis. It will be provided in high-density polyethylene bottles and will be stored according to the instructions on the label.

The probe drug cocktail study drugs will be supplied by Covance, along with the lot numbers. The probe drug cocktail study drugs will be provided in high-density polyethylene bottles (omeprazole and warfarin) and blister packs (caffeine) and will be stored according to the instructions on the package insert.

Vitamin K tablets will be supplied by Covance, along with the lot numbers. The vitamin K tablets will be provided in high-density polyethylene bottles and will be stored according to the instructions on the package insert.

Study drugs will be stored at the CRU in a location that is locked with restricted access.

The bulk drug container and unit dose containers will be labeled in accordance with national laws and regulations. The study drugs will be stored in accordance with the labeling. The study drugs will be transferred from bulk supplies into the subject's dose container by qualified CRU employees. Each unit dose container will be appropriately labeled.

5.2. Study Treatment Administration

Subjects will receive each of the following treatments throughout the study:

- In Period 1, Day 1, 200 mg caffeine (tablet), 40 mg omeprazole (capsule), and 10 mg warfarin (tablet) will be administered as a single dose of probe drug cocktail, along with 10 mg vitamin K (2 × 5 mg tablets), in the morning following a fast of at least

10 hours predose and 2 hours postdose. Water will be restricted for 1 hour prior to and 1 hour after dosing with the exception of water administered for dose administration.

- In Period 2, on Days 6 through 19, oral doses of 200 mg (2×100 mg tablets) LOXO-305 will be administered QD for 14 consecutive days in the morning at the actual time of the Day 1 probe drug cocktail dosing (± 1 hour). On Day 15, LOXO-305 will be coadministered with 200 mg caffeine (tablet), 40 mg omeprazole (capsule), and 10 mg warfarin (tablet) administered as a single dose of probe drug cocktail, along with 10 mg vitamin K (2×5 mg tablets), at the actual time of the Day 1 probe drug cocktail dosing (± 1 hour) following a fast of at least 10 hours predose and 2 hours postdose. On Days 7 through 11, and Days 13, 14, 16, 18, and 19, subjects will fast for at least 2 hours predose and 1 hour postdose. On Days 6, 12, and 17 where clinical laboratory evaluations are performed, subjects will fast for at least 8 hours predose and 1 hour postdose. Water will be restricted for 1 hour prior to and 1 hour after dosing with the exception of water administered for dose administration.

All study drugs will be administered orally with approximately 240 mL of water. An additional 100 mL of water may be administered if needed. Water will be restricted for 1-hour predose and 1-hour postdose, with the exception of water administered for dose administration.

Each unit dose will be prepared by qualified CRU staff.

Appropriate unit dose(s), as described above, will be administered to subjects. Although the timing of events requires that each subject will be administered the appropriate dose at a specific time, the exact dose time of subjects may be staggered to obviate the need to have all subjects on precisely the same study schedule. For each dose, the subject's actual dose time will be recorded in the source documents and transcribed into the eCRF.

Subjects will be instructed not to crush, split, or chew the study drugs.

Subjects will not lay supine for 4 hours following LOXO-305 dose administration, except as necessitated by the occurrence of an AE(s) and/or study procedure(s).

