[REDACTED] Blood samples for concentrations of the substrates (caffeine/paraxanthine, omeprazole, and S-warfarin) in plasma CCI [REDACTED]. Of the samples collected for concentrations of each substrate in plasma predose CCI [REDACTED], samples will be analyzed for concentration of caffeine/paraxanthine CCI [REDACTED], for concentration of omeprazole CCI [REDACTED], and for concentration of S-warfarin CCI [REDACTED].

[figure not shown]
The schematic of the study design is displayed in [Figure 3](#). The start of the study is defined as the date the first subject who is enrolled in the study signs an Informed Consent Form (ICF). Note that enrolled subjects are defined as those subjects who are assigned to receive a dose of study drug; this definition excludes screen failure subjects. Replacement subjects may be enrolled only if deemed necessary by the Sponsor.

Subjects who are determined to be screen failures are permitted to be re-screened if the Investigator (or designee), with agreement from the Sponsor, feels that the subject may meet eligibility criteria upon re-screen. Re-screened subjects will be provided a new subject number.

To assess their eligibility to enter the study, potential subjects will be screened within 34 days (Days -35 to -2) and be admitted to the CRU on Day -1 (Check-in).

Subjects will be confined at the CRU from the time of Check-in (Day -1) until EOT on Day 23 upon completion of all PK and safety assessments or Early Termination (ET) if the subject discontinues. Dosing of probe drug cocktail will occur on Day 1 and Day 15 and dosing of LOXO-305 will occur on Days 6 through 19. A follow-up phone call will occur for all subjects who received at least 1 dose of study drug (including subjects who are terminated early) 7 days (\pm 2 days) after EOT or ET. The duration of participation is expected to be approximately 67 days (Screening through follow-up phone call).

Figure 3: Study Schematic

Abbreviations: EOT = End of Treatment; ET = Early Termination; ICF = Informed Consent Form; PK = pharmacokinetic.

In this study, physical examinations, 12-lead ECGs, vital sign measurements, How Do You Feel? (HDYF?) inquiries, clinical chemistry panel, coagulation parameters, hematology panel, urinalysis (UA; [Appendix 2](#)), and recording of concomitant medications will be performed at specified times during the study (for specific timepoints and details on each study variable, refer to [Appendix 4](#)).

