3.2. Discussion of Study Design

Metabolic routes of elimination, including most of those occurring through the CYP family of enzymes, can be inhibited or induced by concomitant drug treatment. Changes arising from metabolic DDI can be significant and contribute to increases or decreases in the blood and tissue concentrations of the parent drug or active metabolite. Increased or decreased concentrations of a parent drug or its metabolites can alter the safety and efficacy profile of a drug.

The probe drugs chosen in this study allow investigation of DDIs mediated through CYP450 enzymes. LOXO-305 showed no detectable inhibition (IC_{50} CCI μM) of CYP1A2, CYP2B6, and CYP2D6 and showed weak inhibition of CYP2C8, CYP2C9, CYP2C19, and CYP3A4. In vitro LOXO-305 induced CYP3A4, CYP2C19, and CYP2B6 and down regulated CYP1A2. The probe drugs were chosen as they are known to be sensitive substrates of CYP1A2 (caffeine), and CYP2C9 (warfarin), and CYP2C19 (omeprazole). Vitamin K will be administered with warfarin to counteract its anticoagulant effect.

The fixed single-sequence design used in this study is typical for drug interaction studies, because it allows intra-subject comparisons. A single sequence will be used to avoid carry over effects. This study will be open-label because the primary endpoints are not considered subjective.

Conducting the study in healthy adult subjects mitigates the potential confounding effects of the disease state and concomitant medications.

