- e. 12-lead ECGs will be obtained at Screening and Check-in (Day -1), Day 1 (predose), Day 5 (96 hours postdose on Day 1), Day 6 (predose and 2 hours postdose), Day 12 (predose), Day 15 (predose and 2 hours postdose), Day 17 (predose), and Day 20 (24 hours postdose on Day 19), and Day 23 (96 hours postdose on Day 19 [EOT]) or ET. 12-lead ECGs will be collected after the subject has rested in the supine position for at least 10 minutes. When scheduled at the same time as PK blood draws, 12-lead ECGs will be obtained prior to and as close as possible to having blood drawn. The allowed sampling window for 12-lead ECGs is \pm 30 minutes from the nominal timepoint for all postdose 12-lead ECGs and no less than 10 minutes prior to dosing for predose 12-lead ECGs.
- f. Vital sign measurements (supine BP and pulse rate) will be obtained at Screening, Check-in (Day -1), Day 1 (predose), Day 5 (96 hours postdose on Day 1), Day 6 (predose and 2 hours postdose), Day 12 (predose), Day 15 (predose and 2 hours postdose), Day 17 (predose), and Day 20 (24 hours postdose on Day 19), and Day 23 (96 hours postdose on Day 19 [EOT]) or ET. Blood pressure and pulse rate will be measured using the same arm for each reading after the subject has been supine for at least 5 minutes. When scheduled at the same time as PK blood draws, vital sign measurements should be carried out prior to and as close as possible to having blood drawn. The allowed sampling window for vital sign measurements is \pm 30 minutes from the nominal timepoint for all postdose vital sign measurements and no less than 10 minutes prior to dosing for predose vital sign measurements.
- g. Respiratory rate and body temperature will be obtained at Screening, Check-in (Day -1), and Day 23 (96 hours postdose on Day 19 [EOT]) or ET.
- h. Oxygen saturation will be measured via pulse oximetry at Screening, Check-in (Day -1), predose on Day 1, and Day 23 (96 hours postdose on Day 19 [EOT]) or ET. The allowed sampling window for oxygen saturation measurements is \pm 30 minutes from the nominal timepoint for all postdose oxygen saturation measurements and no less than 10 minutes prior to dosing for predose oxygen saturation measurements.
- i. A HDYF? inquiry will be performed at Screening (after the ICF is signed), at Check-in (Day -1), at each postdose vital sign measurement, and at an appropriate time for all other days.

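### The 4-hour no-supine rule follows LOXO-305 dosing only, so it covers the Day 15 cocktail dose but not the Day 1 reference dose, and any posture effect on probe absorption could not be separated from the LOXO-305 effect

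*Protocol*

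**What the plan says.** Protocol Section 5.2 ends with a posture rule: "Subjects will not lay supine for 4 hours following LOXO-305 dose administration, except as necessitated by the occurrence of an AE(s) and/or study procedure(s". Section 3.1 fixes the days. For the cocktail: "Dosing of probe drug cocktail will occur on Day 1 and Day 15". For the study drug under test: "dosing of LOXO-305 will occur on Days 6 through 19". Day 1 is therefore a cocktail day without LOXO-305, and Day 15 is a cocktail day with it.

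The other dosing conditions are matched across the two cocktail days. For Day 1, the fasting and water conditions in Section 5.2 read "10 hours predose and 2 hours postdose. Water will be restricted for 1 hour prior to and 1 hour after dosing with the exception of", the exception being what is drunk with the dose itself. Day 15 has the same fast and water restriction, the same dosing volume (about 240 mL), and a dosing time within 1 hour of the Day 1 time. Appendix 4 footnotes k and l repeat the fasting and water conditions and do not mention posture.

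Footnote e of Appendix 4 lists the supine ECG times, including "Day 1 (predose), Day 5 (96 hours postdose on Day 1), Day 6 (predose and 2 hours postdose), Day 12 (predose), Day 15 (predose and"; the Day 15 entry goes on to a second ECG, 2 hours after the dose. Footnote f gives the same times for vital signs.

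Section 3.2 justifies the design: "The fixed single-sequence design used in this study is typical for drug interaction studies, because it allows intra-subject comparisons". Section 5.3 confirms that the study is non-randomized with one sequence. SAP Section 8.5.3 fits ln AUC0-t, ln AUC0-inf and ln Cmax with treatment as the fixed effect and subject as the random effect.

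**The concern.** A fixed-sequence interaction study isolates the perpetrator's effect only if everything else about the two probe doses is alike. The protocol takes care over food, water and clock time but leaves posture unmatched. On Day 15 subjects must stay off their backs for 4 hours while the probes are absorbed. On Day 1 nothing in the visible text stops them lying down.

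If posture alters the rate of absorption, Cmax would be the parameter most exposed, and it is modelled for every probe. An effect on AUC would need a change in extent of absorption or in clearance, so AUC should be less exposed. Direction matters most for omeprazole. Protocol Sections 1.3 and 1.5 raise possible CYP2C19 induction and lower concentrations, and an upward shift in the Cmax ratio could hide part of a real decrease.

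**Working it through.** The plan states no figure on this point, so there is none to reproduce. The check has three steps.

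**1. Text, side by side**

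| Condition | Day 1 (reference) | Day 15 (test) |
|---|---|---|
| Fast | at least 10 h before, 2 h after | same |
| Water restriction | 1 h before, 1 h after | same |
| Clock time | morning | Day 1 time ± 1 h |
| No-supine rule, 4 h | none (no LOXO-305 given) | applies |
| Supine ECG and vital signs after dosing | none until 96 h | at 2 h |

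Protocol Sections 4.1, 4.2, 4.4, 7.3.3 and 7.3.4 and Appendix 4 footnotes e and f mention the supine position only for ECG or vital signs. Section 7.3 refers to posture only when scheduling procedures. Section 6.2 and the SAP do not mention it.

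**2. Separability**

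Let θ be the true LOXO-305 ratio and f the multiplicative effect of the posture difference. For each subject, the mean of ln(Day 15) − ln(Day 1) is ln θ + ln f, so the model estimates θ × f. The treatment and posture-rule indicators are the same column (0 on Day 1, 1 on Day 15). The matrix [intercept, treatment, posture] has rank 2 of 3. A period term would be aliased in the same way. A simulation with θ = 1, f = 1.10 and n = 16 returned a mean ratio of 1.098, as expected.

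**3. Size under assumptions**

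The documents give no posture effect, so all values of d and p here are assumed. If lying down lowers Cmax by a fraction d, and a proportion p of subjects lie down on Day 1 only, the geometric mean ratio is multiplied by f = (1/(1 − d))^p.

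| d | p = 0 | p = 0.25 | p = 0.5 | p = 1 |
|---|---|---|---|---|
| 0 | 1.000 | 1.000 | 1.000 | 1.000 |
| 0.10 | 1.000 | 1.027 | 1.054 | 1.111 |
| 0.20 | 1.000 | 1.057 | 1.118 | 1.250 |

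If lying down raises Cmax instead, f = (1/(1 + d))^p. At p = 1 this is 1/1.10 = 0.909 for d = 0.10 and 1/1.20 = 0.833 for d = 0.20.

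To compare f with the precision of the study, take n = 16 (Protocol Section 8.1) and assume a within-subject CV, since neither document gives one. The standard error of the mean log difference is √ln(1 + CV²) × √(2/16), and the 90% CI half-width is 1.753 times that (t on 15 df). For CV 25%: √ln(1.0625) = 0.2462; × 0.3536 = 0.0870; × 1.753 = 0.1526; so the interval is the ratio × 0.858 to 1.165. Coverage of the true LOXO-305 ratio by the nominal 90% CI, from the noncentral t with f as a uniform shift, is:

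| CV (assumed) | CI factors | f = 0.90 | f = 0.95 | f = 1.05 | f = 1.10 | f = 1.20 |
|---|---|---|---|---|---|---|
| 15% | 0.912–1.097 | 39.7% | 75.8% | 77.1% | 46.8% | 4.9% |
| 25% | 0.858–1.165 | 68.5% | 84.7% | 85.2% | 72.2% | 36.2% |
| 40% | 0.788–1.270 | 80.9% | 87.8% | 88.0% | 82.5% | 64.1% |

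At f = 1.00 there is no bias and coverage is the nominal 90%.

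**The case against.** The strongest reply is that a gap in wording is not a demonstrated bias. The documents do not prohibit lying down on Day 1, but they do not say that anyone will do so. Nothing in them says that posture affects the absorption of caffeine, omeprazole or warfarin. The rule runs on all 14 LOXO-305 days, 13 of them without the cocktail, and no reason for it is given, so it cannot be read as a rule for standardising probe absorption. Two of the three parameters modelled for every analyte are AUCs. The analysis is estimation without a stated no-effect boundary, and SAP Section 8.1 already advises caution. All of this stands, and it limits what can be claimed about size.

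A reader might infer that the Cmax ratio will be inflated, by at least a few percent and up to 25%. The documents do not support that. The figure of 1.25 needs every subject to lie down on Day 1 and the largest assumed loss. No effect is equally consistent with the text, and so is an effect in the other direction.

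A reader might also infer that posture can disturb only the reference day. That does not hold either: on Day 15 subjects rest supine at 2 hours for vital signs (at least 5 minutes) and an ECG (at least 10 minutes), inside the 4-hour window and under the rule's own exception. Day 1 has no counterpart, and the calculation above ignores this.

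The absence of a Day 1 rule can be confirmed only for visible text. Footnotes m and n of Appendix 4 are redacted, and the Laboratory Manual is separate.

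What the reply does not answer is that the difference, if it has any effect, cannot be removed afterwards and costs almost nothing to prevent.

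**Conclusion.** The mismatch is real. The only visible post-dose posture rule applies to the test cocktail dose and not to the reference dose, and posture is fully aliased with treatment in this design and model. Confidence in that is high.

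Confidence in the size of any bias is low. It rests on two unknowns, how many subjects would lie down on Day 1 and what lying down does to each probe. With a loss of 0 to 20% in 0 to 100% of subjects, the multiplier on the Cmax ratio is 1.00 to 1.25; it falls below 1 if the effect runs the other way. The AUC ratios should be affected less. The 2-hour supine measurements on Day 15 are a second, smaller mismatch. This is an avoidable uncontrolled difference in the primary comparison, probably small, and not evidence that the estimates are wrong.

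**What to change.** Reconcile Protocol Section 5.2 with Appendix 4 footnotes k and l so that the same post-dose posture condition applies to both cocktail doses. One way is to have the existing sentence triggered by administration of the probe cocktail, LOXO-305, or both. The 2-hour supine measurements on Day 15 can be acknowledged in the clinical study report.

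The cost is one sentence and matching footnote text. Subjects are already confined on Day 1 and dosed under staff supervision, so no visit, sample or procedure is added. If Day 1 dosing is already complete, state the limitation in the clinical study report, with actual posture on Days 1 and 15 where it was recorded. No change to the model would help.

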5.3. Randomization

This is a non-randomized study. The study has a fixed treatment sequence.

5.4. Blinding

This is an open-label study.

5.5. Treatment Compliance

The following measures will be employed to ensure treatment compliance:

- All doses will be administered under the supervision of suitably qualified CRU staff.
- Immediately after oral dose administration, a visual inspection of the mouth and hands will be performed for each subject.

- At each dose preparation occasion, a predose and postdose inventory of LOXO-305, caffeine, warfarin, vitamin K, and omeprazole will be performed.

5.6. Drug Accountability

The Investigator (or designee) will maintain an accurate record of the receipt of LOXO-305, caffeine, warfarin, and vitamin K tablets, and the omeprazole capsules received. In addition, an accurate drug disposition record will be kept, specifying the amount dispensed to each subject and the date of dispensing. This drug accountability record will be available for inspection at any time. At the completion of the study, the original drug accountability record will be available for review by the Sponsor upon request.

For each batch of unit doses, the empty used unit dose containers will be discarded upon satisfactory completion of the compliance and accountability procedures. Any unused assembled unit doses will be retained until completion of the study.

At the completion of the study, all unused LOXO-305 tablets will be disposed of by the CRU, in accordance with the CRU's Standard Operating Procedures (SOPs) and local/state/federal guidelines governing waste disposal of investigational drugs, following the Sponsor's written authorization. The caffeine, warfarin, and vitamin K tablets and omeprazole capsules will be disposed of by the CRU in accordance with the CRU's SOPs.

6. CONCOMITANT THERAPIES AND OTHER RESTRICTIONS

6.1. Concomitant Therapies

Paracetamol/acetaminophen (maximum of 2 g/day for up to 3 consecutive days) is an acceptable concomitant medication.

Subjects will refrain from participation in any other investigational study drug trial in which receipt of any investigational drug occurs within 5 half-lives (if known) or 30 days, whichever is longer, prior to Day 1.

All prescription medications and over-the-counter medications including but not limited to: moderate or strong CYP3A4 and/or CYP3A5 inhibitors or inducers (including herbal products such as St. John's wort), CYP2C8 substrates, strong P-gp inhibitors, proton pump inhibitors, antacids, H₂-receptor antagonists, and drugs that prolong QT/QTc interval, herbal products, vitamin supplements, natural or herbal supplements, caffeine (with the exception of caffeine administered for the purposes of this study/in accordance with the protocol), and HRT are prohibited for 14 days or 5 half-lives (if known; except for paracetamol/acetaminophen as referenced above), whichever is longer, prior to Day 1 and through EOT or ET, unless deemed acceptable by the, Investigator (or designee), and Sponsor. Any medication taken by a subject during the course of the study, including details of its dosage, administration, and the reason for its use, will be documented in the eCRF.

The administration of any concomitant medication during the study is prohibited without prior approval of the Investigator (or designee) and Sponsor, unless its use is deemed necessary in a medical emergency. In this case, the use of the concomitant medication will be reported as soon as is practical.

6.2. Diet, Fluid, and Activity Control

Subjects are required to refrain from use of tobacco, smoking-cessation products, and nicotine-containing products and e-cigarettes (nicotine and non-nicotine) within 3 months prior to Screening through EOT or ET.

Consumption of foods or beverages containing grapefruit/grapefruit juice or Seville oranges or its juice within 7 days prior to Check-in (Day -1) and through EOT or ET will not be allowed.

Consumption of alcohol-containing foods or beverages or caffeine-containing foods or beverages (including but not limited to teas [including decaffeinated teas], coffees [including decaffeinated coffees], colas [including decaffeinated colas], energy drinks, gum containing caffeine, chocolate, and foods and beverages containing chocolate]) within 72 hours prior to Check-in (Day -1) and through EOT or ET will not be allowed.

Subjects will refrain from strenuous exercise from 5 days prior to Check-in (Day -1) and during the period of confinement at the CRU and will otherwise maintain their normal level of physical activity through EOT or ET (ie, should not begin a new exercise program or participate in any unusually strenuous physical exertion).

While confined at the CRU, subjects will receive a standard diet at scheduled times that do not conflict with other study-related activities. All study drugs will be administered orally with approximately 240 mL of water. An additional 100 mL of water may be administered if needed.

Fasting requirements and water restrictions in relation to dosing are described in [Section 3.1](#) and [Section 5.2](#).

